10.0 Data Management

- **Confidentiality protection:** The data from test results will be de-identified once it has been collected and before it is stored. This means individual results would not be able to be linked to the participant by others who review the results of this research. The linkage between participant codes and identities as well as all other identifiable

information including consent forms will be stored in a locked room and be accessible only to the study personnel.

- Statistical analysis: For Primary Aim of feasibility and safety, we will compare rates of compliance and device-related adverse events between the treatment and control conditions using the test of non-inferiority. For safety, we will analyze the data using the “intent to treat” paradigm. The meaningful difference in adverse events to detect between the treatment and control is 20% for the following reason. For a regulatory approval, a safety level similar to a comparable FDA-approved device is desired. One such device, with availability of safety data, is a Bioness electrical stimulator for foot drop: It has a 21% higher likelihood for adverse events compared to a standard ankle foot orthosis (Kluding et al. 2013). Based on power analysis below, we will be sufficiently powered to statistically discern different rates of adverse events if more than 3 out of 24 participants experience adverse events in the treatment vs. control condition. In other words, if 3 or less participants out of 24 experience adverse events in the treatment vs. control condition, we will deem TheraBracelet safe for the purpose of an FDA approval. We will verify that there is no order effect using exact binomial tests.
- For feasibility, compliance will be defined as participants’ use of the device for at least half the prescribed time. The reason is that 4 hours/day is still a substantial use of this assistive device in daily living, and will provide sufficiently useful information about feasibility of TheraBracelet. Similarly with the analysis for safety, if 3 or less participants out of 24 are incompliant in the treatment vs. control, we will conclude that TheraBracelet is as feasible as wearing a non-vibrating wristband. The cumulative hours of device usage will also be examined for both conditions to inform the general usage trend.

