- Power analysis: The sample size for the primary outcome of safety was determined for testing hypothesis of non-inferiority using a 2×2 crossover at 80% power and 5% significance level. A sample size of 24 (12 in each condition at randomization) provides sufficient power to conclude non-inferiority within a difference in adverse events of 20% between the discordant pairs (those who are safe with control but unsafe with treatment vs. those with the opposite), assuming a total of 10% discordance rate (proportion of participants with different responses for the two conditions) and a 90% safe rate for the control. That is, we will be powered to statistically conclude non-inferiority (hence safety) if 3 or less out of 24 participants have adverse events in treatment vs. control. For the Secondary Aim involving repeated measures ANOVA, with the effect size of $f=0.25$ for the Box and Block from our previous study, (Seo et al., 2014) a sample size of 19 is needed assuming a conservative correlation of 0.3 across evaluation times, for 80% power and 5% significance level. Thus, we will aim to obtain data from 24 participants. Considering that some may be found ineligible after enrollment, a total of 30 recruitment is proposed.
- Data sharing: Only de-identified coded data will be reported and/or shared with the public in publications, in ClinicalTrials.gov, or upon written request.

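### The count rule of 3 or fewer out of 24 is not the boundary of the plan's own paired non-inferiority test, and the plan does not say which one decides

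*Combined protocol and SAP*

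**What the plan says.** All the relevant text is in Section 10.0 Data Management.

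- **Test.** The Statistical analysis item will compare "rates of compliance and device-related adverse events between the treatment and control conditions using the test of non-inferiority". No test statistic is named.
- **Test parameters.** The Power analysis item gives 80% power, a 5% level (sidedness not stated), 24 participants and a 20% margin. The difference is taken "between the discordant pairs (those who are safe with control but unsafe with treatment vs. those with the opposite". It assumes 10% total discordance and "a 90% safe rate for the control".
- **Count, safety.** The Statistical analysis item rephrases the test as a rule: "if 3 or less participants out of 24 experience adverse events in the treatment vs. control condition, we will deem TheraBracelet safe". The Power analysis item repeats it, saying the study can "statistically conclude non-inferiority (hence safety) if 3 or less out of 24 participants have adverse events in treatment vs. control".
- **Count, compliance.** The same cutoff is carried over: "if 3 or less participants out of 24 are incompliant in the treatment vs. control, we will conclude that TheraBracelet is as feasible".
- **Converse.** The Statistical analysis item also says the study can "statistically discern different rates of adverse events if more than 3 out of 24 participants experience adverse events" in treatment versus control.

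In both places the count is introduced as another way of stating the test. Nothing says which governs if they disagree.

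**The concern.** A count and a test can serve as one criterion only if they accept the same data. Here the count accepts results that the test does not, and on one reading it rejects results that the test accepts. The phrase that sets treatment against control also leaves open whether the 3 is a net excess, the number with events on treatment only, or the raw number with events on treatment.

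Both primary conclusions depend on this. The safety conclusion is meant to support regulatory approval of a device whose month-long use, by the protocol's own account (Section 3.0), has not been studied for safety. With two criteria and no order of precedence, the choice could be made after the results are known. If the count is used, its false-positive rate is not the stated 5%.

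**Working it through.** **Inputs** (Section 10.0): n = 24 pairs; margin 0.20; level 5%; total discordance 10%, taken as 5% + 5% under no true difference; control event rate 10% (from the 90% safe rate). Assumption: the 5% is one-sided, with alternatives shown. Let b = participants with the event on treatment only and c = on control only.

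**1. The plan's sample size.** For a paired score test with discordant rates 0.05 and 0.05, the variance terms are 0.206 at the margin (restricted estimate) and 0.10 under the alternative:

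N = [(1.645·√0.206 + 0.842·√0.10) / 0.20]² = 25.7.

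Exact enumeration first reaches 80% power at n = 23, and gives 82.4% at n = 24. So 24 is consistent with a one-sided 5% paired score test.

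**2. The count's boundary case, b = 3 and c = 0, with no participant having events in both conditions.** This satisfies the count whether the 3 is net, treatment-only or raw. The observed difference is 3/24 = 12.5%.

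- *Wald:* upper limit = (b − c)/n + z·√[(b + c) − (b − c)²/n]/n = 0.125 + 1.645·√(3 − 9/24)/24 = 0.125 + 1.645 × 0.0675 = **23.6%**. At one-sided 2.5% it is 25.7%; at one-sided 10% it is still 21.2%.
- *Score:* with c = 0 the restricted control-only rate is 0, so z = (24 × 0.20 − 3)/√(24 × 0.20 × 0.80) = 1.8/1.96 = 0.92, p = 0.18; upper limit **27.5%**.
- *Other methods:* Bonett-Price 25.2%; exact binomial 29.2%.

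Every version exceeds 20%.

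**3. Chance of declaring safety when the true excess is exactly 20 points.**

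| Criterion | Setting | Declared safe |
|---|---|---|
| Net excess, b − c ≤ 3 | treatment-only 20%, control-only 0% | 26.4% |
| Net excess | 25%, 5% | 30.3% |
| Net excess | 30%, 10% | 32.8% |
| Raw count, X ≤ 3, X ~ Bin(24, p) | control 0%, p = 0.20 | 26.4% |
| Raw count | control 5%, p = 0.25 | 11.5% |
| Raw count | control 10%, p = 0.30 | 4.2% |
| Raw count | control 15%, p = 0.35 | 1.3% |
| Raw count | control 20%, p = 0.40 | 0.35% |
| Paired score test, one-sided 5% | control-only 0% to 10% | 3.3% to 4.7% |
| Paired Wald test, one-sided 5% | control-only 0% to 10% | 6.4% to 11.5% |

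**4. The raw count also errs the other way.** Suppose four participants have events in both conditions and nobody is discordant. The raw count is 4, so the rule fails. The observed difference is zero and the paired score upper limit is 10.1%. With an equal 20% event rate in both conditions, the raw count passes only P(X ≤ 3 | 24, 0.20) = 26.4% of the time.

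**5. Which results pass the score test at one-sided 5%.** Upper limits for (b, c): (1,0) 16.7%, pass; (2,1) 19.1%, pass; (2,0) 22.3%, fail; (3,0) 27.5%, fail; (3,1) 24.4%, fail; (3,2) 21.3%, fail. By Wald, (2,0) passes at 17.6% and (3,2) at 19.4%; (3,0) and (3,1) still fail. (3,3) passes by both.

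**The case against.** The best defence is that the wording speaks of participants who have events, not of an excess, so the 3 is the raw treatment count. That reading gives the assumed 90% control safe rate a use, since the paired test does not need it once discordance is fixed. At a 10% control rate it gives 4.2% error and a 78.6% pass rate, close to the stated 5% and 80%. Above 10% the rule becomes stricter, not more lenient. This stands as far as it goes: the 26% to 33% range belongs to the net-excess reading and should be quoted only with that condition.

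It does not restore equivalence. The raw count works only at one control rate, ignores the control events actually observed, and still accepts 3 versus 0, where the paired test fails. Section 9.0 says the control condition is there to account for natural worsening, and a raw count discards that information.

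It can also be said that the plan attaches its conclusions to the count, so the count governs. In that case the named test, margin and level decide nothing, and the count remains a wrong translation of them.

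Three smaller points are fair. Disagreement covers only part of the range: 1 versus 0 and 3 versus 3 pass both the net count and the test. In the 3 versus 0 case the test fails to show non-inferiority; it does not show harm. For compliance, the plan's appeal to the safety analysis may be meant to carry over the 20-point margin, but no control non-compliance rate is given, so the raw-count reading has no basis there.

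**Conclusion.** The concern holds. The count is not the boundary of the paired test at one-sided 2.5%, 5% or 10%, and no standard method tried at one-sided 5% makes it so. At 3 versus 0 the count declares safety while the upper limit is 23.6% to 29.2% against a 20-point margin.

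If the count is used, its error at a true 20-point excess depends on an undefined reading: 26% to 33% as a net excess (control-only rate 0% to 10%), or 4.2%, 11.5% and 26% as a raw count at control rates of 10%, 5% and 0%. At worst that is five to six times the stated 5%. The same defect applies to compliance.

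The sentence about discerning different rates when more than 3 have events is also wrong in kind: failure to show non-inferiority is not evidence of a difference.

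These figures rest on 24 complete pairs and the stated margin. The sample size is not at fault. This must be fixed before analysis because the primary decision rule contradicts itself.

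**What to change.** In Section 10.0, Statistical analysis and Power analysis:

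1. Remove the 3-or-fewer sentences as decision criteria for safety and compliance, and remove the sentence on discerning different rates.
2. Make the paired test the sole criterion, for example: *non-inferiority is concluded if the one-sided 95% upper limit (paired score method) for (participants with the event on treatment only − participants with the event on control only)/n is below 20 percentage points.*
3. State that the 5% level is one-sided.
4. State the margin for compliance: 20 points, if the safety margin is meant to carry over.
5. If an illustrative count is wanted, derive it from the test. With the score method, 1 versus 0 and 2 versus 1 pass; 2 versus 0 and 3 versus 0 do not.

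Another paired method is acceptable if it holds its level at n = 24. Simple Wald does not (6.4% to 11.5%).

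**Cost.** Wording only; no new data or participants. The criterion is stricter than the net-excess count: under the plan's 5%/5% discordance the pass rate falls from 98.7% to 82.4%. Against the raw count at a 10% control rate it moves from 78.6% to 82.4%. The stated 80% power is met only at one-sided 5%. It is 62.9% at one-sided 2.5%, and 64.5% at one-sided 5% if total discordance is 20%.

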3.0 Intervention to be studied

Device: A stand-alone prototype is composed of an MP3-playing watch and a vibrator (see the pictures below; total weight 40g, watch=3.7cm×5.3cm). Both items are off-the-shelf products (i.e. available to purchase for anyone). The vibrator is attached to the wristband of the watch. The vibrator's wire is connected to the MP3 player via an audio jack. The MP3 player drives the vibrator with its internal battery for at least 22 hours, enabling a full day of use after an overnight charge. The MP3 player/watch is charged using a conventional phone charger. The MP3 player can play any file including the treatment vibration file with white noise vibratory signal at the intensity that is 40% below the sensory threshold (i.e. subthreshold, imperceptible to the participant) and control file with zero amplitude (i.e. no vibration).

FDA: The use of the vibrator for this proposed purpose of affecting the hand sensation and/or dexterity has not been approved by the FDA. The vibrator is a general-purpose vibrator, not specifically designed for any particular purpose. Safety of using this vibrator at the proposed intensity (40% below the person's sensory threshold, i.e. imperceptible) for a month has not been studied, and will be studied as a primary aim of the proposed research. Currently there is no vibration exposure guideline for this small level of vibration. People are exposed to higher-intensity, suprathreshold vibration daily (e.g. from a phone, riding a car).

Control/placebo: No vibration will be the control condition. The MP3 player will play a zero-amplitude file, producing no vibration.

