9.0 Study Design / Methods

- **Study design:** The study will use a 2×2 crossover design. Participants will be randomly assigned to either the treatment or control condition for the first month, followed by a 2-week washout period and then crossover to the other condition. For both conditions, participants will be instructed to wear TheraBracelet on the affected wrist every day for at least 8 hours/day during their daily activity over a month. The device will apply wrist vibration at 60% of the sensory threshold (imperceptible) for the treatment condition, and no vibration for the control condition. The control condition is needed to assess safety of TheraBracelet in comparison to that of simply wearing a wristband, thereby accounting for any worsening of symptoms that may occur as a natural course after stroke. Half the participants will start with the treatment and half with the control (balanced).
- **Schedule:** One person's participation will be 2.5 month long (= 1 month for one condition, 2 week washout period, 1 month for another condition). For each condition, participants will come to the laboratory once a week for evaluation for a total of 5 times: The 1st visit will entail the baseline evaluation followed by an introduction to using the device. Subsequent visits will be for evaluation after using the device each week. A follow-up assessment will be administered 4-16 weeks after the 10th session if any safety measure has worsened as defined as an adverse event by the 10th visit compared to the 1st visit. The follow-up assessment will evaluate only the measure that has worsened.
- Evaluation will include feasibility, safety, and durability, as detailed below.

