12.0 Risks to Subjects

There is a slight risk for loss of confidentiality. There is a minor risk of physical and mental fatigue from engaging in the study activity. The treatment a person receives at one time point may be less beneficial than the other study treatment. There is a minor risk of skin irritation from wearing the wristband and/or from vibration. There is a minor risk of discomfort in moving the arm/hand due to the weight of the device on the wrist, although the device weighs only 40g. Potential risks that may be associated with use of wrist vibration all day every day for a month will be tested as the primary outcome measures of safety within the study. These risks are: deterioration of hand sensation, strength, and dexterity, increased upper limb pain level, spasticity level, and/or wrist skin irritation. Occurrence of these adverse events are expected to be rare because the intensity of vibration used in TheraBracelet is subliminal while we are exposed to higher-intensity, suprathreshold vibration daily (e.g. from a phone). TheraBracelet has also been used during hand task practices in chronic stroke survivors for a total of 6 hours over 2 weeks without reportable adverse events in the PI's current study. However, there has not been a study that focuses on safety of TheraBracelet. Currently there is no known information regarding any side effects associated with using this small imperceptible (unfelt) level of vibration all day every day for a month. Currently there is no vibration exposure guideline for this small level of vibration.

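### Vibration-on versus vibration-off of the same worn device supports a conclusion about added vibration, not the whole-device safety verdict drawn from it

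*Combined protocol and SAP*

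**What the plan says.** The two conditions differ only in the file played. In the control condition, "The MP3 player will play a zero-amplitude file, producing no vibration" (Section 3.0), and the wearing instruction is common: "For both conditions, participants will be instructed to wear TheraBracelet on the affected wrist every day for at least 8 hours/day" (Section 9.0). Section 9.0 gives the control two purposes. The first is that "The control condition is needed to assess safety of TheraBracelet in comparison to that of simply wearing a wristband"; the second is given as "thereby accounting for any worsening of symptoms that may occur as a natural course after stroke".

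Section 9.0 counts skin irritation and swelling as safety events, alongside sensation, strength, dexterity, pain and spasticity, each judged against baseline. Section 12.0 recognises that wearing itself carries risk: "There is a minor risk of skin irritation from wearing the wristband and/or from vibration". It also lists discomfort from the weight on the wrist.

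The only formal safety analysis, in Section 10.0, is to "compare rates of compliance and device-related adverse events between the treatment and control conditions using the test of non-inferiority". On the margin, Section 10.0 says: "The meaningful difference in adverse events to detect between the treatment and control is 20% for the following reason". The reason given is a foot-drop stimulator whose adverse events were 21% more likely than with an ankle foot orthosis. The decision rule follows: "if 3 or less participants out of 24 experience adverse events in the treatment vs. control condition, we will deem TheraBracelet safe". The power analysis in the same section works with discordant pairs and treats a non-inferior result as equivalent to safety. Section 1.0 also promises a comparison of adverse event frequency with the approved stimulator, but Section 10.0 gives no test or decision rule for it.

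**The concern.** The test and the verdict answer different questions. The test asks whether switching vibration on adds more than 20 percentage points to the event rate of people already wearing the device. The verdict names the whole device. Allowing for the natural course after stroke is a sound reason to have the control for sensation, strength, dexterity, pain and spasticity. Irritation under a wristband is not part of that natural course. It is an effect of the device, and it is present in both months.

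The source of the margin widens the gap. The stimulator figure compares one device with a different one, not a device with itself switched off. Passing an on-versus-off test at a similar margin therefore does not show safety comparable to the approved device. At stake is the main conclusion of the primary safety aim: a device that irritates many wearers in both months could be declared safe on the strength of a contrast that does not register it.

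**Working it through.** **Inputs (Section 10.0).** N = 24; margin Δ = 0.20; 5% level (sidedness not stated); 80% power; 10% total discordance, taken as 5% each way under no true difference; 90% control safe rate. The documents give no rate of wear-related harm, so the rates *w* below are assumptions.

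**1. The plan's own figure.** Let *b* be the participants with an event in the treatment month only, and *c* those with an event in the control month only. The paired score statistic is

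z = (b − c − NΔ) / √[N(2q + Δ − Δ²)],

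where q is the constrained maximum-likelihood estimate of the control-only probability. Non-inferiority is concluded if z ≤ −1.645. Exact enumeration with both discordant probabilities at 0.05 gives 82.4% power at N = 24. The asymptotic version gives 76.9% at 24 and needs 26. At one-sided 2.5% the exact power is 62.9%. The planned 24 is thus reproduced by a one-sided 5% paired score test.

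**2. What the contrast measures.** Let p11 be the probability of an event in both months, p10 in treatment only and p01 in control only. The difference in event rates is (p11 + p10) − (p11 + p01) = p10 − p01. Events in both months drop out. Harm from wearing alone is equally likely in each month, so p10 = p01 and its expected contribution is zero.

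**3. Two patterns of wear harm, no vibration effect, N = 24.**

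- *Recurrent:* a fraction *w* is harmed in both months, and the 5%/5% discordance applies to the rest, so p10 = p01 = 0.05(1 − w). At w = 50% this is 0.025.
- *Independent between months, no background events:* p10 = p01 = w(1 − w). At w = 10% this is 0.09; at w = 50% it is 0.25.

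| Assumed *w* | Recurrent: chance of passing | Independent: chance of passing |
|---|---|---|
| 0% | 82.4% | 100% (no events at all) |
| 10% | 84.4% | 67.8% |
| 20% | 86.3% | 49.8% |
| 30% | 88.3% | 43.2% |
| 50% | 92.3% | 39.3% |

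Recurrent harm makes passing more likely because fewer participants are left to be discordant. Independent harm makes it less likely because discordant pairs add variance. Neither column measures how much harm wearing does.

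**4. The count of 3.** Suppose the rule means a net excess with no opposite pairs: b = 3, c = 0, so q = 0. Then z = (3 − 4.8)/√(24 × 0.16) = −1.8/1.96 = −0.92, which fails. For b = 2, z = −2.8/1.96 = −1.43, which fails; for b = 1, z = −3.8/1.96 = −1.94, which passes. A net-excess-of-3 rule also passes 26% to 30% of the time when the true excess is 20 points (0% and 5% opposite pairs respectively). Read instead as an absolute count in the treatment month, at most 3 of 24 is met with probability 78.6%, 26.4%, 4.2% and 0.4% at true rates of 10%, 20%, 30% and 40%. The two readings are different rules.

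**The case against.** A reader might infer that wear harm always cancels and can never block the safety verdict. The documents do not support that. Cancellation is exact only for harm recurring in the same person; otherwise it holds on average, and the added discordance can defeat the test. If 3 of 24 is an absolute count, wear harm counts directly. That reading has some support: the one-sided 95% exact upper bound is 29.2% for 3/24 and 34.2% for 4/24, so 3 is the largest count below 10% + 20 points = 30%. Against it, the rule is worded as treatment versus control and tied to a discordant-pair calculation. The ambiguity stands.

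Nor should a reader quote a constant 82.4% whatever the harm in both months. That fixes discordance at 10% while the control safe rate leaves the planned 90%: with 10%, 30% or 50% harmed in both months plus 5% in control only, it is 85%, 65% or 45%. The recurrent scenario above also departs from 90%; it is illustrative.

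It can fairly be said that Section 9.0 frames the control as a comparison with wearing a wristband, and that Section 11.0 speaks of the safety of the vibration. On that reading the contrast is the intended one, which supports narrowing the conclusion, not keeping the broad one. Section 9.0 already scores irritation and swelling against baseline and includes a physician interview about wearing the device. Section 1.0 grades events by severity and device relevance. The monitoring board sees all events by condition and may recommend stopping. These are real safeguards, but none enters the rule that yields the final verdict.

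**Conclusion.** The concern holds in a limited form. The paired test can support a statement about what vibration adds to wearing the device. It cannot by itself support a statement that the device is safe, and Section 10.0 makes that step. Wear harm has zero expected effect on the contrast, and recurrent harm never counts against the device: the chance of passing goes from 82.4% with none to 92.3% with half of participants affected in both months. Harm that varies between months can still block the verdict (67.8% passing at 10%, 39.3% at 50%), but through noise rather than detection of harm. These figures rest on assumed harm rates, no vibration effect, and the one-sided 5% score test that reproduces the planned sample size. The design and data collection are adequate; the defect lies in the inference, the reporting and the undefined count.

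**What to change.** In Section 10.0, in both the analysis and power paragraphs:

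- Word the paired conclusion as: vibration adds no more than 20 percentage points to the adverse event rate of wearing the device.
- Report the proportion with any event, and separately with wear-related events (skin irritation, swelling, wrist or arm discomfort), in each condition and in either month, with exact confidence intervals. For these summaries, score against the baseline taken before the device was first worn, so that harm carried over from the first month is not absorbed into the second baseline.
- Base any whole-device safety statement, including the comparison with the approved stimulator promised in Section 1.0, on those absolute rates, and state how that comparison will be made.
- State whether 3 of 24 is an absolute, net or discordant count, and reconcile it with the 20% test, which a net excess of 3 with no opposite pairs does not pass.

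If the sponsor wants an absolute limit, it is for the sponsor to justify. The 30% used above is only an illustration: its 10% component is a planning assumption for the composite event, not an acceptability limit.

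The cost is revised wording and a few exact intervals. The downside is a narrower formal conclusion, with wear-related rates shown openly and with wide intervals at 24 participants.

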1.0 Objectives / Specific Aims

- Objectives: To determine the feasibility and safety of using this assistive device, TheraBracelet, every day during waking hours, and to determine if TheraBracelet's instant effects are sustained during prolonged use.
- Design: Community-dwelling chronic stroke survivors will be randomly assigned to either the treatment or control condition for the first month, followed by a 2-week washout period and then crossover to the other condition. In both the treatment and control conditions, participants will be instructed to wear the device for at least 8 hours/day every day during their normal daily activity and come to the laboratory for evaluation prior to and each week of using the device (for a total of 5 evaluations over 4 weeks). The device will deliver vibration (treatment) or no vibration (control). Double-blinding will be possible because the treatment vibration is imperceptible (i.e., subthreshold).
- Primary Aim: Determine the feasibility and safety of using TheraBracelet daily for a month. For feasibility, compliance in using the device will be assessed by weekly self-reports of usage. Hypothesis: TheraBracelet will have a feasibility level comparable to wearing a non-vibrating wristband. To determine safety, participants will be examined at each weekly visit for any worsening of hand sensation, dexterity, grip strength, upper limb pain, spasticity, and wrist skin irritation. Adverse events will be recorded and categorized by severity (minor, moderate, and serious) and device relevance (related to device use or not). Adverse event frequency will be compared between conditions, and with a comparable FDA-approved device, Bioness electrical muscle stimulator. Hypothesis: TheraBracelet will have a safety level equivalent to or better than the comparable FDA-approved assistive device.

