detectable change (MDC) (also known as the smallest real difference, Chen et al 2009). Hand dexterity will be determined to have deteriorated if the Nine Hole Peg or Box and Block Test score worsens by more than 20% (approximately 2 standard deviation of the population data) and MDC (Chen et al 2009). Hand strength and dexterity measurement will be performed three times during the baseline testing. Upper limb pain will be assessed using the visual analog pain rating scale (0 to 10). Upper limb pain will be determined to have increased if the pain level indicated on the visual analog pain rating scale increases by more than 2. Spasticity will be show assessed using the Modified Ashworth Scale (MAS). Spasticity will be determined to have worsened if MAS increases by more than 1 point (equivalent to the effect size of botulinum toxin A). Wrist skin irritation and increased swelling, if there is any, will be noted. Rigorous safety criteria will be used in which adverse events will be noted if any of the measures (hand sensation, strength, dexterity, pain, spasticity, skin irritation, swelling) worsens at any of the four evaluation times compared to the baseline. The co-investigator and study neurologist, [name], will meet with each participant in person or via teleconference to interview the participant regarding safety related to wearing the device.

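### Adverse events are graded by severity, but the safety verdict counts affected participants whatever the grade, so an unqualified finding of safety can coexist with serious device-related events

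*Combined protocol and SAP*

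**What the plan says.** The Primary Aim in Section 1.0 sets up the grading: "Adverse events will be recorded and categorized by severity (minor, moderate, and serious) and device relevance".

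Section 9.0 (Safety) defines what counts: "adverse events will be noted if any of the measures (hand sensation, strength, dexterity, pain, spasticity, skin irritation, swelling) worsens". Each of the four visits after baseline is judged this way. Strength, dexterity, pain and spasticity carry numeric thresholds. Skin irritation and swelling do not: "Wrist skin irritation and increased swelling, if there is any, will be noted".

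Section 10.0 (Statistical analysis) keeps device relevance but not severity: "we will compare rates of compliance and device-related adverse events between the treatment and control conditions using the test of non-inferiority". The verdict follows. When no more than three of the 24 participants are affected, treatment against control, the plan states: "we will deem TheraBracelet safe for the purpose of an FDA approval". The power analysis in the same section is built "to conclude non-inferiority within a difference in adverse events of 20% between the discordant pairs", and repeats the cut-off of 3 out of 24 as the point at which safety is concluded.

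**The concern.** Two attributes of each event are to be recorded, severity and device relevance. Only the second reaches the analysis. The test, the margin, the cut-off and the power assumptions all treat a participant under a given condition as safe or unsafe, so one participant with minor skin irritation weighs the same as one with a serious event.

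The verdict is worded without qualification and is aimed at a regulatory reader. If serious device-related events occurred on treatment, the pre-specified sentence could still be written, and the information most relevant to it would have had no part in reaching it.

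**Working it through.** **Inputs.** From Section 10.0: n = 24 in a crossover, margin m = 0.20, total discordance 10%, power 80%, significance level 5%, cut-off of 3 participants. Assumptions of this check: the discordance splits equally (5% and 5%), the test is one-sided, and the cut-off carries the restriction to device-related events stated earlier in the same paragraph. The plan names no specific paired test. A score test with restricted maximum-likelihood variance is used here.

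**1. The plan's own figure.** n = [z(0.95)·√v0 + z(0.80)·√v1]² / m², with v1 = 0.10, v0 = 2p + m − m², and restricted estimate p = 0.0231, so v0 = 0.0462 + 0.20 − 0.04 = 0.2062.

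n = (1.645 × 0.4541 + 0.842 × 0.3162)² / 0.04 = 25.7, so 26 against the stated 24. Exact power of this test at n = 24 is 82.4%. The sample size is therefore reproduced closely, and no input to it refers to severity.

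**2. The count rule, read literally, with no events under control.**

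- Three participants with serious device-related events: 3/24 = 12.5%. The cut-off is met and the device is deemed safe. The exact one-sided 95% upper bound for 3/24 is 29.2%.
- Four participants with only minor skin irritation: 4/24 = 16.7%. The cut-off is exceeded. That this means not safe is the implied converse of the rule; the plan ties more than 3 to discerning different rates.
- At a true rate of 20%, the chance of 3 or fewer out of 24 is 26%.

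**3. The paired test.** Let b be participants with an event on treatment only and c those with an event on control only. z = (b − c − n·m) / √[n(2p + m − m²)], with p re-estimated for each pair of counts. When c = 0, p = 0. For 1 versus 0 this gives (1 − 4.8) / √(24 × 0.16) = −3.8 / 1.960 = −1.939.

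| b vs c | z | one-sided p | non-inferior at 5% |
|---|---|---|---|
| 1 vs 0 | −1.939 | 0.026 | yes |
| 2 vs 1 | −1.721 | 0.043 | yes |
| 2 vs 0 | −1.429 | 0.077 | no |
| 3 vs 0 | −0.919 | 0.18 | no |

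Grade enters nowhere. In the 2 versus 1 row, both treatment-only participants may have serious events and the control-only participant minor irritation. Conversely, 2 versus 0 fails even if both events are minor.

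**4. Sensitivity.** At one-sided 2.5%, 1 versus 0 narrowly fails, but 1 versus 1 (p = 0.014) and 2 versus 2 (p = 0.024) pass. With a Wald limit at one-sided 5%, 2 versus 0 passes and 3 versus 0 fails. The number tolerated moves with the method; indifference to grade does not.

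**5. What no serious events would show.** The exact one-sided 95% upper bound for 0/24 is 1 − 0.05^(1/24) = 11.7%.

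**The case against.** The strongest reply has four parts.

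- **Safeguards exist.** Under Section 11.0 the safety board sees condition assignment and individual data every 3 months and may recommend stopping; the study physician may recommend that a participant discontinue; all adverse events are reported. Section 9.0 adds an interview with the study neurologist. This stands, and a reader should not infer that the trial would overlook serious harm. But these provisions act on conduct and disclosure, and none changes the sentence that declares safety.
- **The rule is comparative.** It sets treatment against control, and the control wristband accounts for irritation from wearing the band. This also stands. A reader might infer that any four participants with trivial irritation fail the device. They do so only if the four are in excess of control.
- **The formal test is stricter than the count.** A reader might infer that three serious events pass the plan's non-inferiority test. They do not when set against none under control (p = 0.18). The example rests on the stated count rule. Under the test the problem remains at smaller counts.
- **Magnitude is already built into most components.** Numeric thresholds for strength, dexterity, pain and spasticity do screen out small changes. They do not separate a moderate from a serious event, and irritation and swelling have no threshold.

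A reader might also infer that minor events will dominate the count. The plan gives no rates by type or grade, and Section 12.0 expects the listed events to be rare, so that is not supported.

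**Conclusion.** The concern holds in this form: severity is to be recorded but has no role in the safety verdict, so the plan as written permits an unqualified statement of safety when serious device-related events have occurred on treatment. The size depends on which rule governs: up to 3/24 (12.5%, upper bound 29.2%) under the literal count with no control events; 1 versus 0 or 2 versus 1 discordant participants under the score test. These figures rest on the one-sided 5% level, the 0.20 margin and the device-related reading of the cut-off. They show what the rule allows and predict nothing about what will happen.

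The plan does not contradict itself here, since Section 1.0 promises a comparison of event frequency and Section 10.0 supplies one. The defect is that a conclusion about frequency is worded as a conclusion about safety. It should be corrected, but it does not invalidate the trial.

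**What to change.** Amend the Statistical analysis text of Section 10.0 in three respects:

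1. State that the non-inferiority result concerns the overall frequency of participants with device-related adverse events, and nothing more.
2. Report, by condition, the number of participants with serious and with moderate-or-worse device-related events, each with an exact confidence interval. If no serious event is seen, give the 11.7% upper bound beside the conclusion.
3. State that the unqualified safety wording will not be used if any serious device-related event, graded blind to condition, occurs on treatment; such events will be described next to the non-inferiority result instead.

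The third item is a judgement about wording, and the sponsor may prefer another severity criterion, provided it is fixed before unblinding. It qualifies the claim and does not turn a single event into a failed trial.

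The cost goes a little beyond rewording. The available text neither defines the three grades nor says who assigns them, so definitions and a blinded grading step must be written in advance. One serious device-related event on treatment would then qualify the headline claim. Sample size, visits, treatment and monitoring are unaffected.
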